Clinical outcomes of intravenous vitamin C synergy with Tyrosine kinase inhibitor in lung adenocarcinoma patients with epidermal growth factor receptor mutations

November 14, 2018

Study Protocol and Statistical Analysis Plan

Background:

Vitamin C (VitC) infusion are widely used by integrative and complementary cancer practitioners for many years. In the last 10 years, many studies have shown that pharmacological concentrations of VitC can selectively kill tumor cells. A series of in vitro experiments [1], animal experiments [2-4] and Phase I-II clinical trials [5-7] have successively confirmed that VitC at pharmacological concentrations has the effect of inhibiting the growth of various tumors, including lung cancer.

Our Phase I clinical study, "The safety and pharmacokinetics of high dose intravenous ascorbic acid synergy with modulated electrohyperthermia in Chinese patients with stage III -IV non-small cell lung cancer", confirmed the safety of high-dose vitamin C in combination with deep hyperthermia in advanced non-small cell lung cancer, the concentration is as high as 1.5g/kg.d, 3 times a week. There were no significant adverse reactions. And it can significantly improve the quality of life (QoL). Our Phase II clinical trial in 2018 confirmed that IVC + mEHT treatment can significantly improve QoL, prolonge progression free survival (PFS) and overall survival (OS), and moderate cancer-related inflammation in advanced NSCLC patients. The article is already in the submission stage.

Recently we noticed that patients with epidermal growth factor receptor (EGFR) mutation who were taking tyrosine kinase inhibitor (TKI) with intravenous VitC every week had a relatively longer drug resistance time in our oncology center. We believe that it is necessary to observe whether intravenous VitC simultaneously with TKI can prolong the time of drug resistance in patients with EGFR mutations.

Objectives:

The purpose of this study was to investigate the effect of intravenous VitC in combination with TKI on the tumor size, QoL, PFS and OS in lung adenocarcinoma patients with EGFR mutation

Inclusion Criteria:

- Primary non-small cell lung cancer (adenocarcinoma) with EGFR mutations on exons 19 and 21.
- 18 years old to 75 years old.
- During the trial, patients were prescribed TKI (received initial treatment within 2 months, or change medication within 2 months) and did not receive chemotherapy or radiotherapy at the same time.
- Eastern Cooperative Oncology Group(ECOG) performance status are 0 to 2.
- Expected survival over 3 months.
- Household registration is Guangdong Province.

Exclusion Criteria:

- Co-morbid conditions that affect survival: end stage congestive heart failure, unstable angina, myocardial infarction (within the past 6 weeks), and uncontrolled blood sugars of greater than 300 mg/dL, known chronic active hepatitis or cirrhosis.
- Glucose-6-phosphate dehydrogenase deficiency (G6PD) (a relative contraindication).

- Patients who are allergic to VitC.
- Patients with HIV and other infectious diseases.
- Patients who are taking anticoagulants and have coagulopathy;
- Combine dysfunction of important organs such as heart, lung, liver and kidney;
- Patients with impaired renal function (serum creatinine content > 1.2 mg/dL)
- Compromised liver function with evidence of Serum total bilirubin content, ALT and AST > 2 times normal reference value.
- Pregnant or lactating female.
- Smoking and alcohol abuse patients;
- Anti-infective treatment is required for systemic or localized serious infections;
- Patients with hyperuric acidosis (normal: 91-456 $\mu\text{mol} / 24\text{h}$ (8-40mg / 24h));
- Wilson's disease.
- Evidence of significant psychiatric disorder by history or examination that would prevent completion of the study or preclude informed consent.
- Any condition that impairs the patients' ability to swallow, which impairs drug absorption or drug kinetic parameters, including any kind of gastrointestinal resection or surgery;
- History of surgery of visceral organs within 6 weeks before the trial.

Study design:

Experimental period: 12.05.2018~31.12.2019

Method:

In experimental group:75 patients received a weekly intravenous Vitamin C injection (dose: 30 g / time, once a week, treatment termination when the disease progress is confirmed) in combination with daily TKI; In the control group:75 patients received only TKI daily. (dose: Osimertinib 80 mg/d, or Tarceva 150 mg/d, or Iressa 0.25 g/d.)

Outcome:

Primary outcome was PFS. Secondary outcome include: OS, QoL, tumor size.

Observations and assessments:

To evaluate the effects of the above treatments on patient safety, tumor size, tumor markers, inflammatory factor levels, quality of life, progression-free survival and overall survival time. General information was collected before and after treatment, and the QoL was assessed on the quality of life questionnaire (QLQ-C30) scale. Chest CT enhancement, brain MRI, liver color Doppler ultrasound, adrenal gland ultrasound, blood test for liver and kidney function, blood and urine routine, tumor markers, tumor necrosis factor, interleukin-6 level were checked every month.

Statistical methods:

The effect of treatment on PFS, OS was analyzed by using Kaplan-Meier probability estimates. Comparison of tumor markers and immune factors was performed using t-test.

Key issues to be addressed:

To explore whether intravenous VitC can prolong resistance time of TKI on lung adenocarcinoma patients with EGFR mutations. To observe whether the combination treatment can benefit NSCLC patients.

Expected results:

Intravenous VitC in combination with TKI can significantly prolong the time of drug resistance, improve the quality of life, and have a positive effect on the prognosis of lung adenocarcinoma patients with EGFR mutations.

Safety measures and emergency plan:

Diarrhea, rash, liver dysfunction and other adverse reactions may occur during the treatment, but the above reactions will be eliminated under the doctor's treatment. If patients experience any discomfort during the study, or if there is a new change in the condition, or any unforeseen circumstances, whether or not related to treatment, patients should promptly notify their doctor, who will make a judgment and medical treatment. If the condition of the disease changes to a certain standard (if the condition progresses), the trial may be terminated earlier after discussion by the research group.

Reference

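### The third inclusion criterion depends on treatment received during the trial and no analysis population is stated, so patients given chemotherapy or radiotherapy could be left out after entry, which can bias PFS in either direction

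*Combined protocol and SAP*

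**What the plan says.** Under Inclusion Criteria, the third item begins "During the trial, patients were prescribed TKI" and ends with the condition that they "did not receive chemotherapy or radiotherapy at the same time". A parenthesis between the two ties the TKI to a start or a change within two months.

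Method describes the arms by treatment received: "In experimental group:75 patients received a weekly intravenous Vitamin C injection" and "In the control group:75 patients received only TKI daily". It describes no allocation procedure and no masking. The rule "treatment termination when the disease progress is confirmed" is attached to the vitamin C infusion; whether the TKI also stops at that point is not said.

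Outcome states: "Primary outcome was PFS. Secondary outcome include: OS, QoL, tumor size". For the time-to-event endpoints, Statistical methods says only that "The effect of treatment on PFS, OS was analyzed by using Kaplan-Meier probability estimates". It gives no analysis population, no censoring rule and no handling of other anticancer treatment. Safety measures and emergency plan adds that on a change in condition "the trial may be terminated earlier after discussion by the research group", without saying whether the patient concerned stays in the analysis.

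**The concern.** An inclusion criterion should be decidable when the patient enters. This one is decided partly by what happens afterwards. A patient who is eligible on day one and later has radiotherapy added to continuing TKI no longer satisfies it as worded. A control patient in that position no longer matches the Method description of the control group either. An analyst who follows the text could leave such patients out, and nothing in the plan prevents it.

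PFS is primary, and chemotherapy or radiotherapy is likely to be started because the tumour is growing. The patients at risk of being left out are therefore disproportionately those with events. One arm has weekly infusions and the other does not, so the decision to add treatment can be made with the arm known. The share left out could then differ between arms.

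**Working it through.** **What can be reproduced.** The only design figure is 75 + 75 = 150 patients. The plan gives no alpha, power, hazard ratio, event count, median PFS or rate of chemotherapy or radiotherapy, so there is no stated result to check. The calculation below shows scale only.

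**Inputs.**
- From the plan: 75 per arm, and a study period ending 31 December 2019. The start date can be read day first (598 days / 30.4375 = 19.6 months) or month first (391 / 30.4375 = 12.8 months, run as 12.9).
- Assumed: exponential PFS with a median of 11 months in both arms, uniform accrual over 6 months, two-sided alpha 0.05, log-rank test, and a share q of progressors left out of each arm.

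**Closed form, 19.6 months, no true effect.**
- Hazard: λ = ln 2 / 11 = 0.0630 per month. Follow-up C is uniform from 13.6 to 19.6 months.
- Proportion progressing: P = 1 − [exp(−13.6λ) − exp(−19.6λ)] / (6λ) = 1 − (0.4244 − 0.2908) / 0.3781 = 0.647. This is about 97 events in 150 patients.
- Mean time at risk per patient: M = P/λ = 10.26 months.
- Part of M contributed by progressors: M₁ = M − E[C·exp(−λC)] = 10.26 − 5.80 = 4.46 months.
- Event rate after leaving out a share q of progressors: r(q) = (1 − q)P / (M − qM₁).
- r(0.1) = 0.582 / 9.815 = 0.0593, an implied median of ln 2 / 0.0593 = 11.7 months.
- r(0.3) = 0.453 / 8.923 = 0.0507, an implied median of 13.7 months.
- With 30% left out of the vitamin C arm and 10% out of control: HR = 0.0507 / 0.0593, about 0.855. Reversed: 1.17.
- Patients left out: 75 × 0.647 × (0.3 + 0.1) = 19.4.

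**Simulation on the same assumptions** (4,000-5,000 runs per setting, no true effect; HR is the ratio of event rates):

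| Left out, control / vitamin C | HR, 19.6 months | HR, 12.9 months | Type I error, 19.6 months |
|---|---|---|---|
| 0 / 0 | 1.00 | – | 0.049 |
| 10% / 10% | 1.00 | 1.00 | 0.057 |
| 30% / 30% | 1.01 | 1.01 | 0.054 |
| 10% / 20% | 0.94 | – | 0.059 |
| 20% / 10% | 1.07 | – | 0.060 |
| 10% / 30% | 0.85 | 0.81 | 0.106 |
| 30% / 10% | 1.17 | 1.22 | 0.104 |

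In the last two rows nearly all false positives fall on one side: 0.102 of the 0.106 favour vitamin C, and all but 0.006 of the 0.104 go against it. The simulation agrees with the closed form.

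Equal shares leave the contrast alone but still lengthen both curves. The medians implied by the event rates rise from 11 to 11.7 months at 10%, and to about 13.6 months at 30%.

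With a true HR of 0.70 and the 19.6-month period, equal 30% removal gives 0.67. Leaving out 30% of vitamin C and 10% of control progressors gives 0.57; the reverse gives 0.82.

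These runs model progression only. No OS figure was calculated.

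**The case against.** The strongest reply is that no removal rule exists. Nowhere does the plan say that a patient who starts chemotherapy or radiotherapy is excluded, withdrawn, replaced or censored. The item may be a loosely worded entry condition, or a restriction on concomitant treatment with patients kept in the analysis. Its parenthesis is anchored to entry, and the document uses the past tense throughout, so tense alone proves little. This stands: removal is a possibility, not a stated procedure.

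The closing phrase of the item can also be read as limited to time on TKI. Treatment given after the TKI has stopped would then not breach it. That narrows the PFS problem and largely removes the OS problem. It does not remove the PFS problem, because the only stopping rule at progression is attached to vitamin C, and treatment added to continuing TKI would still breach the criterion. The plan gives no frequency for that.

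Finally, the shares are assumed, and only the 30% versus 10% split brings the type I error to about 0.10. At 20% versus 10% it is about 0.06, and with equal shares it is close to nominal. This also stands.

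A reader might infer that the plan deletes progressing patients, or that it is tilted towards vitamin C. Neither is supported: no text orders deletion, and the reverse imbalance moves the hazard ratio the other way. Nor can one speak of losses after a described allocation step, since the plan describes none; entry is the safer reference point.

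**Conclusion.** The concern holds in a limited form. The criterion is written on conduct during the trial, cannot be fully checked at entry, and is not overridden by any stated analysis population. Applied literally, it would select patients on a post-entry event that is likely to be linked to the primary endpoint. That is more than an omitted detail.

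The consequence is a possible bias of unknown direction. Any removal of progressors flatters PFS in the arm concerned. The comparison shifts materially only if the shares differ. In the assumed 30% versus 10% case, the null hazard ratio moves to about 0.81-0.85 or 1.17-1.22 and the type I error roughly doubles. The removal shares, the 11-month median and the 6-month accrual are all assumptions. Unqualified bias in OS would be too strong a claim: it depends on reading the criterion to cover treatment after progression.

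**What to change.** 1. Under Inclusion Criteria, judge eligibility on the patient's status at entry only.
2. Have the authors reconcile separately whether the wording is also meant to restrict concomitant treatment during the trial. Nothing proposed here changes that restriction.
3. Add to Statistical methods: *The primary analysis of PFS and OS includes every enrolled patient in the assigned group. Chemotherapy or radiotherapy started after entry does not remove a patient, and follow-up continues to progression and death. PFS censored at the start of such treatment is a sensitivity analysis only.*

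For the third step, the group must be recorded at entry, since the plan describes no allocation procedure. The cost is a few sentences of protocol and analysis-plan text. There are two small downsides: patients who start other treatment must still be followed, and the estimate then includes the effect of that treatment.

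### The exclusion for hyperuric acidosis names what reads as a uric acid condition, but its normal range fits a substance of about 88 g/mol, so name and limit do not describe the same analyte

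*Combined protocol and SAP*

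**What the plan says.** In the Exclusion Criteria, one line bars "Patients with hyperuric acidosis (normal: 91-456" µmol/24h, followed by the same range in mass units, 8-40 mg/24h. The line names no specimen and states no explicit excluding value; the cut-off is implied as a result above the upper normal limit.

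The same list has a separate kidney criterion, "Patients with impaired renal function (serum creatinine content > 1.2 mg/dL", and a general exclusion for dysfunction of major organs including the kidney.

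Under Study design, Method, the experimental arm is described as "75 patients received a weekly intravenous Vitamin C injection (dose: 30 g / time, once a week", continued until progression is confirmed, alongside a daily TKI. The control arm is 75 patients on a TKI alone.

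The Observations and assessments section lists monthly blood tests of liver and kidney function and routine blood and urine tests. It lists no 24-hour urine collection and names neither uric acid nor oxalate.

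**The concern.** When one range is printed in both µmol and mg, the reader can work out which substance it belongs to. Here both ends point to about 88 g/mol. The condition name points elsewhere: hyperuric acidosis is not a standard analyte name, and the nearest reading is a raised uric acid, at about 168 g/mol. The name and the numbers cannot both be right.

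This line decides who may enter the trial. Staff who follow the name would order uric acid and compare it with limits that cannot both be uric acid limits. Staff who follow the numbers have to guess the analyte. Either way the intended exclusion may not operate, and the enrolled population may differ from the one described.

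**Working it through.** **Inputs.** From the Exclusion Criteria: 91-456 µmol/24h and 8-40 mg/24h. Not in the documents: molar masses, built here from standard atomic weights (C 12.011, H 1.008, N 14.007, O 15.999).

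**1. Implied molar mass.** Formula: molar mass (g/mol) = mg × 1000 / µmol.

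- Low end: 8000/91 = 87.91
- High end: 40000/456 = 87.72

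The two ends agree, so the two versions of the range are consistent with each other.

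**2. Allowance for rounding.** Let every printed figure be off by up to half a unit.

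- Low end: 7500/91.5 = 81.97 to 8500/90.5 = 93.92
- High end: 39500/456.5 = 86.53 to 40500/455.5 = 88.91
- Consistent with both ends: 86.53 to 88.91

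**3. Candidate substances.**

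| Substance | Formula | g/mol | Low-end interval | High-end interval |
|---|---|---|---|---|
| Uric acid | C5H4N4O3 | 168.11 | outside | outside |
| Oxalate ion | C2O4 | 88.02 | inside | inside |
| Oxalic acid | C2H2O4 | 90.03 | inside | outside |

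Uric acid is 168.11/87.91 = 1.91 times too heavy.

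**4. Converting the range back.** µmol to mg: µmol × molar mass / 1000. mg to µmol: mg × 1000 / molar mass.

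| Substance | 91-456 µmol becomes | 8-40 mg becomes |
|---|---|---|
| Uric acid | 15.3-76.7 mg | 47.6-237.9 µmol |
| Oxalate ion | 8.0-40.1 mg | 90.9-454.5 µmol |

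Oxalate reproduces the printed figures closely; uric acid does not.

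**5. Effect on eligibility if uric acid is measured.** The upper limit is 40 mg by one unit and 76.7 mg (456 µmol) by the other. A patient excreting 50 mg/24h has 50000/168.11 = 297 µmol/24h, which is above normal in mg and normal in µmol. Every value between 40 and 76.7 mg/24h gives opposite answers depending on the unit the laboratory reports. This step needs no outside reference range and no assumption about oxalate.

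**The case against.** The other side accepts the arithmetic and disputes how much it matters.

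- **The name is only an interpretation.** Uric acid is the nearest reading of a non-standard term, and the English has slips elsewhere, so a translation error is plausible. This stands, and it is why the point is worded as a mismatch and not as a wrong uric acid range. The line still needs correcting. A PDF reading error is unlikely, because four printed numbers agree on one molar mass.
- **Other safeguards exist.** The creatinine and organ-dysfunction exclusions remain, and kidney function and routine urine are checked monthly. These reduce renal risk, but they are separate measures and do not perform this screen.
- **Higher doses have been given.** The Background reports phase I use of 1.5 g/kg three times a week without significant adverse reactions. Assuming a body weight of 50-80 kg, that is 1.5 × 3 × 50 = 225 to 1.5 × 3 × 80 = 360 g per week, or 7.5-12 times the present 30 g. This tempers the concern about dose. It does not settle safety in the patients this line would exclude, because that study's eligibility rules are not shown.
- **The harm is inferred.** The documents do not say what risk the line guards against. The study looks local and run by its authors, who may know what they meant, and nothing shows that the line was misapplied. All of this is fair. But a protocol has to be usable by others, and the text does not tell them which test to order.
- **A molar-mass match does not validate a clinical range.** Correct: agreement with oxalate does not show that 91-456 µmol/24h is the right normal range or cut-off for it. The fix takes this into account.

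**Conclusion.** The point holds: the line is wrong as written. Its numbers belong to a substance of 86.5-88.9 g/mol, and uric acid, at 168.1 g/mol, cannot be that substance under any rounding of the printed figures. Nothing else in the documents resolves the conflict.

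The conclusion rests on two things outside the text: molar masses calculated from chemical formulas, and the reading of the condition name as a uric acid disorder. That oxalate was intended is probable from the arithmetic but remains an inference.

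All 150 planned patients (75 + 75) have to pass this criterion, and 75 of them receive the infusions. How many would be wrongly admitted or excluded cannot be estimated, because the documents give no distribution of the test result and no number screened. Confidence is high for the mismatch and lower for its clinical consequence. As a safety exclusion that cannot be applied consistently, it should be fixed. It does not touch sample size, power, type I error or the PFS analysis.

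**What to change.** The clinical lead should rewrite this one line so that it names the analyte, the specimen and the excluding value. Which analyte was meant is a clinical decision.

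- **If urinary oxalate was meant:** call the condition hyperoxaluria, specify a 24-hour urine collection, confirm that the printed range is valid for oxalate and, if so, exclude above 456 µmol/24h (40 mg/24h).
- **If uric acid was meant:** replace both ranges with a valid uric acid range, check that the two units agree at 168.1 g/mol, and state the excluding value.

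In either case, name the test among the screening procedures so that staff know to order it.

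The cost is an amendment to one eligibility line, with no change to design, sample size or analysis. If patients have already been screened under it, check which analyte was measured and against which limit.

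### Nothing in the plan keeps those who judge progression from knowing the arm, and progression has no criteria or dating rule, so later calling in the VitC arm could bias PFS towards VitC

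*Combined protocol and SAP*

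**What the plan says.** The document is a combined protocol and SAP. The relevant statements are these.

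- **Outcome:** "Primary outcome was PFS". No definition, start date, assessor, dating rule or censoring rule follows.
- **Study design, Method:** "75 patients received a weekly intravenous Vitamin C injection" on top of daily TKI, with "treatment termination when the disease progress is confirmed". For the control group, "75 patients received only TKI daily". No placebo or sham infusion is described.
- **Observations and assessments:** the tests include "Chest CT enhancement, brain MRI, liver color Doppler ultrasound, adrenal gland ultrasound", and the list ends "tumor necrosis factor, interleukin-6 level were checked every month". The schedule is the same for both arms. The section does not say who reads the scans or what they know.
- **Safety measures and emergency plan:** "If the condition of the disease changes to a certain standard (if the condition progresses), the trial may be terminated earlier after discussion by the" (the sentence ends by naming the study team as the body that discusses it). The standard is not given. The same section has patients report a change in condition to their doctor, who judges it.
- **Background and Expected results:** the centre reports having noticed longer time to resistance with weekly VitC, and the plan expects VitC to prolong it.

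Blinding, masking, independent review and response criteria are not mentioned anywhere.

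**The concern.** Progression on imaging is a judgement, and borderline scans can be called now or at the next visit. Three features of this plan combine. The arm is visible to patients and treating staff. The investigators have written down which result they expect. And no rule limits the judgement. Requiring confirmation without saying more also leaves open whether the event is dated to the first suspicious scan or to the one that confirms it, which is a difference of about one month under the monthly schedule.

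If borderline calls are put off more often in the VitC arm, PFS there lengthens with no drug effect. The result would look like the one the trial was set up to find. An analysis of the recorded dates alone could not separate the two explanations.

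**Working it through.** **Nothing to reproduce.** The plan gives 75 patients per arm without a derivation. It states no alpha, sidedness, power, hazard ratio, median PFS or event count, and names only Kaplan-Meier estimates for PFS. The check therefore asks how much late calling in one arm could matter.

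**Inputs from the document:** 75 v 75; monthly assessment in both arms; an experimental period of 12.05.2018 to 31.12.2019, which is about 12.9 months if it starts on 5 December 2018 and about 19.6 months if it starts on 12 May 2018.

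**Assumptions, none from the document:** exponential PFS with median 10 or 14 months in both arms (true HR = 1); uniform accrual over 6 months; log-rank test at one-sided 2.5%; a share p of VitC-arm events recorded one scan late.

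**Steps for each simulated trial**

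1. Draw the event time from an exponential with mean (median / ln 2) and round it up to the next monthly scan.
2. Add one month to a random share p of VitC-arm times.
3. Censor at the last scan before the cut-off.
4. Compute the log-rank O − E and V for the VitC arm. The apparent HR is exp[mean of (O − E)/V] over runs. A false positive favouring VitC is (O − E)/√V < −1.96.

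A second set of runs (2,000 per setting) used medians of 8, 12 and 18 months, with window/accrual of 13/6 or 19.5/12 months.

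| VitC-arm calls one scan late | Apparent HR, main set | False positive favouring VitC, main set | Apparent HR, second set | False positive favouring VitC, second set |
|---|---|---|---|---|
| 25% | 0.96-0.98 | 3-4% | 0.96-0.98 | 3.0-3.8% |
| 50% | 0.92-0.96 | 3-6% | 0.92-0.95 | 3.8-5.6% |
| 100% | 0.85-0.92 | 6-10% | 0.84-0.89 | 6.1-11.5% |

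With no late calling, the second set gives HR 0.99-1.01 and 1.8-2.8% favouring VitC. That agrees with the nominal 2.5%: the simulation error is about 1.96 × √(0.025 × 0.975 / 2000) = 0.7 percentage points.

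**Two scans late (second set).** In half of VitC patients: HR 0.85-0.91, false positives favouring VitC 5.3-10.5%. In all of them: HR 0.70-0.81 and 10.5-31.1%.

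**Why a one-scan delay has a limited effect.** Exponential PFS has a constant hazard. If every VitC-arm call is one scan late, that arm has no event at the first scan and the same hazard as control at each later scan. The whole bias is then the control events expected at scan 1: 75 × (1 − 2^(−1/10)) = 5.0 for a 10-month median, or 75 × (1 − 2^(−1/14)) = 3.6 for 14 months.

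**Limit of the check.** The simulation delays every VitC-arm event. Deaths cannot be called late, so the 100% row is an upper case for a one-scan delay.

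**The case against.** The strongest reply is that the effect is small unless late calling is widespread. With a quarter of calls one scan late, the false-positive rate favouring VitC is 3-4% against 2.5%, and monthly imaging in both arms keeps each slip to about a month. No document supports any particular share, and the error rates belong to a test the plan does not name. All of this stands, and it limits the size of the point. It does not supply the missing criteria or dating rule.

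A reader might also infer more than the document supports:

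- **That the scan readers do know the arm.** The plan does not say who reads the scans or what they are told. It supports only that nothing prevents their knowing.
- **That the VitC arm has its own incentive to wait.** The stop at confirmed progression is written for the infusion. The plan does not say what happens to the TKI at progression in either arm, so a difference in incentive cannot be established.
- **That masking the existing readers would remove the bias at no extra staffing.** Masking cannot supply criteria. Changes judged by the treating doctor or discussed by the research group do not pass through an image reader. Liver and adrenal ultrasound are done with the patient present, who may disclose the arm. If the treating doctor also reads the scans, that person cannot be masked.
- **That the bias could never be detected later.** If CT and MRI images are kept, a masked re-reading could test for it, and OS does not depend on scan reading.

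**Conclusion.** The point holds as a weakness in how the primary endpoint is protected. Progression is undefined and undated, the arms are open in effect, assessment is not masked, and the stated expectation favours VitC. Late calling in the VitC arm would bias PFS towards VitC.

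The bias is slight if a quarter of calls slip by one scan and modest at a half. It becomes material when late calling is near-universal or exceeds one scan. These sizes rest on the assumed medians, accrual, exponential PFS and log-rank test. The document does not show that late calling occurred or would occur. The change is worth making because it is cheap and because a dating rule chosen after results are seen would not be credible. How patients are allocated is also not described, but that is a separate matter which masking does not address.

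**What to change.** Add to Observations and assessments:

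> Imaging requests carry the study number only, and those who read the monthly CT and MRI are not told the arm. For the PFS analysis, progression is RECIST 1.1 progression on these masked readings, with target lesions fixed at baseline, or death, dated to the first scan that shows it (or to the date of death). PFS by treating-physician date is a sensitivity analysis.

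In the same place, state how ultrasound findings and clinically judged progression count in PFS, and how patients who stop before a masked call are censored. The text concerns the dating of the endpoint only and leaves the rule for stopping treatment as it is.

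**Cost.** A short protocol addition and a request-form rule, with no placebo, added scan or change in sample size. No added reader is needed if the scan readers are separate from the treating doctors; the document does not say, so the sponsor should confirm it. Masked and treating-physician dates will sometimes differ, and both must be reported. Ultrasound and clinical calls may remain unmasked, so some risk of bias stays.

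### Three TKIs and two TKI histories are pooled, with neither recorded before the arm is assigned nor balanced or adjusted for, so the PFS contrast can reflect a different mix

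*Combined protocol and SAP*

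**What the plan says.** All references are to the combined protocol and SAP.

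- **Study design, 'Method'.** The experimental arm has weekly intravenous vitamin C plus a daily TKI: "In experimental group:75 patients received a weekly intravenous Vitamin C injection". The control arm has the TKI alone: "In the control group:75 patients received only TKI daily". The agents are listed as alternatives, "dose: Osimertinib 80 mg/d, or Tarceva 150 mg/d, or Iressa 0.25 g/d". The list stands after the control-arm sentence, and I read it as applying to both arms. No rule says which patient receives which agent.
- **'Inclusion Criteria'.** Two TKI histories are eligible: "received initial treatment within 2 months, or change medication within 2 months". The reason for a change is not restricted. The text does not say what the two months are counted from.
- **'Outcome'.** "Primary outcome was PFS. Secondary outcome include: OS, QoL, tumor size".
- **'Statistical methods'.** "The effect of treatment on PFS, OS was analyzed by using Kaplan-Meier probability estimates". No test, stratification factor, covariate or display by TKI or line is named.
- **'Key issues to be addressed'.** The question is about resistance to the TKI itself: "To explore whether intravenous VitC can prolong resistance time of TKI on lung adenocarcinoma patients with EGFR mutations".

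The document describes no allocation method, blinding or stratification, and does not require TKI or line to be recorded before the arm is assigned.

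**The concern.** The trial asks whether vitamin C delays resistance to a TKI. Which TKI is taken, and whether it is the patient's first, bear plausibly and directly on that outcome. If the vitamin C arm holds more patients from the group with longer PFS, the two Kaplan-Meier curves separate even when vitamin C is inert. A mix in the other direction can hide a real effect. Nothing in the plan makes the mix similar in the two arms, and nothing in the analysis removes the consequence of a difference.

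There is also a question of interpretation. With initial and changed treatment combined and no results by stratum, a reader cannot tell whether a result concerns a first TKI or a later one.

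**Working it through.** **The plan's own figure.** The documents give 75 per arm, 150 in total, without alpha, power, hazard ratio or event target. The figure can be neither reproduced nor refuted, and this point does not depend on it.

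**1. Apparent hazard ratio when vitamin C has no effect**

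Assumptions, none from the documents: exponential PFS; median 10 months in the shorter-PFS stratum and 15 or 20 months in the longer (ratio 1.5 or 2.0); censoring at 18 months; longer-stratum shares centred on 50%, for example 60% v 40% for a 20-point difference.

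In an arm with share p of the longer stratum, the survival function is S(t) = p·exp(−λ₁t) + (1−p)·exp(−λ₀t), where λ₀ = ln 2/10 and λ₁ = λ₀/ratio. The unadjusted hazard ratio for arm is the root of the large-sample Cox score equation for these two mixtures.

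| Difference in mix | Shares | HR, ratio 1.5 | HR, ratio 2.0 |
|---|---|---|---|
| 10 points | 55% v 45% | 0.961 | 0.934 |
| 20 points | 60% v 40% | 0.923 | 0.873 |
| 30 points | 65% v 35% | 0.886 | 0.815 |

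**2. How often chance alone would produce such differences**

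Take simple randomisation, 75 per arm and a 50% share. The SD of the difference in shares is √(2 × 0.25/75) = 0.082, so 95% of trials fall within 1.96 × 0.082 = 0.16, or 16 points.

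The exact probabilities use the fact that the difference in counts plus 75 is binomial(150, 0.5):

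- At least 10 points: 0.10 × 75 = 7.5, so 8 or more patients. Probability 0.22.
- At least 20 points: 0.20 × 75 = 15 patients. Probability 0.018.
- At least 30 points: 0.30 × 75 = 22.5, so 23 or more patients. Probability 0.0002.

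So 10 points is ordinary chance, 20 is uncommon and 30 is very rare. The larger differences would arise mainly from non-random allocation.

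**3. What stratifying the analysis does**

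A simulation used 75 v 75 patients, 4,000 runs per scenario and a true vitamin C hazard ratio of 1. Its assumptions were a median of 10 months in the shorter stratum, a hazard ratio of 0.45, 0.60 or 0.75 between strata, uniform accrual over 6 months, and cut-off at 12.9 or 19.7 months. The two cut-offs correspond to the two ways of reading the start date.

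| Expected shares | Apparent HR, unstratified | False-positive rate, unstratified |
|---|---|---|
| 50% v 50% | 0.99–1.00 | 4.4%–5.7% |
| 60% v 40% | 0.85–0.95 | 5.7%–11.9% |
| 80% v 20% | 0.63–0.84 | 10.4%–55.4% |

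The log-rank test stratified by the same factor gave hazard ratios of 0.99 to 1.02 and false-positive rates of 4.4% to 5.7% in every scenario, including 80% v 20%. The last row is a stress test of the remedy; nothing in the documents suggests so large an imbalance.

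**The case against.** The case on the other side is substantial, and four parts of it stand.

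- **A mixed background is not itself a bias.** Under true randomisation the unstratified test keeps its size, as the first row of the simulation table shows. Adding vitamin C to whichever TKI is prescribed is a legitimate pragmatic question, and 'Key issues to be addressed' asks about TKIs in general. With randomisation, what would remain is chance imbalance, lost precision and unclear interpretation. The larger risk of bias comes from the absence of any described allocation method.
- **The TKI may be fixed at entry.** A reader might infer that the plan lets the TKI be chosen once the arm is known, since the arms are visibly different. The documents do not show this. The criterion that "patients were prescribed TKI (received initial treatment within 2 months, or change medication within 2 months" reads most naturally as a TKI started or changed around or before entry. The order relative to assignment is unstated, and that is all that can be said. Line is in any case patient history.
- **A change of medication need not follow resistance.** A reader might take it that way, but no reason for change is given. Change after failure of an earlier TKI is simply not excluded.
- **The effect sizes are not in the documents.** They do not say how strongly TKI or line affects PFS, nor that either is already captured for each patient; 'Observations and assessments' mentions only general information.

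None of this supplies the missing step. Even if every TKI was set before entry, the plan neither balances TKI and line between arms nor adjusts for them.

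**Conclusion.** The point holds as an omission. Followed as written, the plan gives an unadjusted comparison of PFS and OS, pooled over three TKIs and two TKI histories, with no described allocation that would make the arms alike in either. The contrast can therefore reflect a different mix. The documents do not show that it will.

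The size is conditional on the assumed median ratio of 1.5 to 2.0: about 0.96 to 0.93 at 10 points, 0.92 to 0.87 at 20 and 0.89 to 0.82 at 30. Only the first is a common result of chance. Confidence is high for the omission and limited for its magnitude. The change should be made: it is specific and inexpensive, and in simulation it removed the distortion from a recorded baseline factor.

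**What to change.** 1. In 'Method', require the TKI and its line (initial or changed medication, with the reason for change) to be recorded before the arm is assigned.
2. In 'Statistical methods', compare PFS and OS with a log-rank test and Cox model stratified by TKI and by initial v changed medication. Fix the TKI grouping in advance, for example osimertinib v Tarceva/Iressa, and show PFS by stratum.
3. Once an allocation method is stated, use the same strata for allocation. Items 1 and 2 can be written now, although stratified analysis cannot correct for unrecorded differences between arms that were not randomised.

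The cost is protocol wording and two entry fields. With the example grouping there are 2 × 2 = 4 strata for 150 patients. A sparse cell may need merging, by a rule fixed in advance. All three agents and both histories can stay; no view is given on which TKI or dose should be used.
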